3.2. Schema

[figure not shown]

Figure 1:Study ALXN1840-HV-105 Schematic

Participants will be admitted on Day -1 of each period for Check in procedures. Eligible participants will be randomized on Day 1 immediately prior to dosing in Period 1.

Participants will receive treatment (A or B) based on randomization on Day 1 of each period. Blood samples for PK analysis of total Mo (as a measure of ALXN1840) and celecoxib will be collected in each period on Day 1 at pre-dose, 1, 2, 3, 4, 5, 6, 8, 12 and 24 hours (Day 2) and then at 24 hour intervals on Days 3, 4, 5, 6, 7, 8, 9, 10, and Day 11. The nominal 336-hour sample for Period 1 will be collected pre-dose in Period 2. Participants will be discharged on Day 11 of each period after completion of all procedures and review of all safety data. The end of study visit (EOS) will occur on Day 15 ± 2 of Period 2, with the collection of 336-hour PK sample for Period 2.

Participants may be asked or required to stay in the CRU between Periods 1 and 2, and/or before the EOS visit, for their own safety, and also to maintain the integrity of the conduct of the study.

3.3. Study Endpoints

3.3.1. Primary Endpoints

The primary endpoints include following PK parameters of celecoxib with and without the coadministration of ALXN1840

- C_{max}: maximum observed plasma concentration
- AUC_t: area under the plasma concentration (AUC) versus time curve from time 0 to the last quantifiable concentration
- AUC_w: AUC versus time curve from time 0 to infinity

3.3.2. Secondary Endpoints

The secondary endpoints include following PK parameters for plasma total Mo with the coadministration of celecoxib and safety assessed parameters

- The PK parameters
 - C_{max}
 - AUC_t
 - AUC_{∞}

- The safety parameters
 - Incidence of treatment-emergent adverse events (TEAEs) and treatmentemergent serious adverse events (TESAEs)
 - Physical examination (PE)
 - Vital signs measurements
 - Clinical laboratory results
 - 12-lead ECG results

4. General Statistical Considerations

All data captured on the case report form (CRF), laboratory safety variables, and PK assessments will be listed on an individual basis by treatment sequence and participant. Summary tables will be presented by treatment and overall, unless otherwise specified.

All pre- and post- dose assessments including repeated and/or unscheduled assessments will be included in the data listing.

Continuous variables will be described using the following descriptive statistics: number of non-missing values (n), arithmetic mean, standard deviation (SD), median, Q1, Q3, IQR, minimum, and maximum, unless otherwise specified. Categorical variables will be summarized using percentages and frequency count.

For the summary statistics of all continuous variables unless otherwise specified, minimum and maximum will be presented to the same number of decimal places as the raw data, mean, median, Q1, Q3, and IQR will be presented to one more decimal places than the raw data, and SD will be presented to two more decimal places than the raw data.

Percentages will be suppressed when the count is zero and will be presented to one decimal place. The denominator for all percentages will be the number of participants in the treatment sequence for the population of interest, unless otherwise specified.

Baseline is defined as the last non-missing assessment (including repeated and unscheduled assessments) prior to treatment on Day 1 (dose day for each period), unless otherwise specified. If there are repeated assessments at a time point, the first non-missing assessment will be included in the summary tables. If the original scheduled measurement at that time point is missing, the next available repeated measurement will be used in the summary tables.

For safety laboratory evaluations, for the purpose of summarization, any numeric values recorded below the lower limit or above the upper limit of quantification will be set to the respective limit for all related summaries. In listings, original results containing inequality sign will be displayed, unless otherwise specified.

Study day will be calculated as follows:

If assessment date is on or after the dose of treatment, then

•

Study Day = Assessment Date – Day 1 Date + 1

• Otherwise,

Study Day = Assessment Date – Day 1 Date

All statistical analyses detailed in this statistical analysis plan (SAP) will be conducted using SAS[®] Version 9.4 or higher (SAS Institute, Inc., Cary, North Carolina) and Phoenix[®] WinNonlin[®] Version 8.0 or higher (Certara USA, Inc., Princeton, New Jersey).

4.1. Statistical Hypotheses

The primary objective is to determine the effect of ALXN1840 on the PK of celecoxib. There is no formal null hypothesis to be statistically tested and used to drive declaration of study success or failure.

To assure the study has enough participants, to estimate the inhibitory effect of ALXN1840 on the metabolism of celecoxib, the sample size was determined using the conservative 90% confidence interval (CI) and 80% to 125% no-effect boundary approach described in the FDA Guidance "Clinical Drug Interaction Studies —Cytochrome P450 Enzyme- and Transporter-Mediated Drug Interactions" (2020). This guidance notes the 80 to 125% boundaries represent a very conservative standard for drugs that have wide safety "margins" and "the totality of evidence should be taken into consideration when determining the clinical impact of the DDI on the substrate drug". Therefore, if the estimated inhibition effect of ALXN1840 on celecoxib PK lies outside this no-effect boundary, this should not be interpreted as a failed study.

4.2. Sample Size

A default of no-effect boundary (80% to 125%) approach will be employed to assess whether there is an inhibition effect on the metabolism of celecoxib in the presence of ALXN1840. For a 2-period crossover study design, assuming the true ratio of the means (celecoxib + ALXN1840 vs celecoxib alone) on the PK parameters is 1 (C_{max} ; AUC_{∞}) and the intra-participant coefficient of variation (CV) is 0.30 (Dennison, 2018), a total sample size of 32 participants can achieve 90% power with two 1-sided tests, each with a type I error rate of 5% (two-sided type I error rate of 10%). The intra-participant CV is estimated using residual mean-square error (MSE) term in the analysis of variance (ANOVA) model. The CV is estimated as 100% × $\sqrt{(exp (MSE) - 1)}$ for the log-transformed PK parameters. Assuming a 15% dropout rate, approximately 38 participants will be enrolled.

4.3. Randomization, Stratification, and Blinding

This is a randomized, open-label, 2-period, 2-sequence, cross-over study. The randomization will be stratified by sex. In an effort to achieve balance between males and females in each sequence, there will be no less than 16 and no more than 22 of either sex (ie, a maximum split in either direction of approximately 60%:40%).

4.4. Analysis Set

4.4.1. Enrolled Set

The enrolled set will include all participants who sign the informed consent form (ICF).

4.4.2. Pharmacokinetic/Pharmacodynamic Analysis Set

The PK analysis set will include all participants who have sufficient plasma samples to have evaluable PK data for celecoxib and/or total Mo (as a measure of ALXN1840) in plasma.

The Pharmacodynamic (PD) analysis set will include all participants who have sufficient plasma samples to have evaluable PD data for total Cu or PUF Cu.

4.4.3. Safety Set

The safety set will include all participants who receive at least 1 dose of study intervention.

5. Participant Disposition

5.1. Disposition

Using the enrolled set, the screen failure of participants will be summarized with counts and percentages by overall. Summary table will include the following:

- Number of participants in the enrolled set (ie, all participants who signed the ICF)
- Number of participants who were screen failures
- Number of participants who were randomized
- Number of participants who failed screen due to COVID-19 related reasons
- Reason for screen failure that was not due to eligibility

Based on the randomized participants, the analysis sets will be summarized with counts and percentages by treatment and overall. Summary table will include the following:

- Number of participants included in PK/PD analysis set
- Reason for exclusion from the PK/PD analysis set
- Number of participants included in safety set
- Reason for exclusion from the safety set

Using the randomized participants, PK analysis set, and safety set respectively, the disposition of participants will be summarized with counts and percentages by treatment and overall. Summary table will include the following:

• Number of participants who completed the study

- Number of participants who discontinued the study
- Reasons for discontinuation
- Number of participants who discontinued the treatment
- Reasons for treatment discontinuation
- Number of participants who were discontinued due to COVID-19

Screen failure data, participant disposition data, and analysis set will be presented in separate data listings for the participants who randomized.

5.2. Protocol Deviations

The protocol deviations will be summarized by treatment and overall for the safety set.

All protocol deviations will be presented in a data listing based on randomized participants.

6. Demographics and Baseline Characteristics

6.1. Demographics and Baseline Characteristics

Age, sex, race, ethnicity, height, and body mass index (BMI) will be collected at Screening; weight will be collected at Screening and Check-in for each period.

Demographic characteristics including age, sex, race, ethnicity, weight (kg), height (cm), and BMI (kg/m²) will be summarized by treatment sequence and overall for the safety set.

Weight measurements collected at Check-in to Dosing Period 1 will be used as baseline for the summary.

Demographic characteristics will be presented in a data listing for the safety set.

6.2. Urine Alcohol and Drug screen

Urine alcohol test and urine drug screen will be performed at Screening and Check-in for each period.

Urine alcohol and drug screen results in the safety set will be presented in a data listing for the safety set.

6.3. Medical History

Medical history will be collected at Screening.

Medical history results will be presented in a data listing for the safety set with each verbatim term be mapped to a system organ class (SOC) and preferred term (PT) using the Medical Dictionary for Drug Regulatory Activities (MedDRA, Version 23.0 or later).

6.4. Inclusion and Exclusion Criteria

Inclusion and exclusion criteria will be confirmed at Screening and Check-in for each period.

Admission criteria deviations are defined as any violation of protocol-defined inclusion/exclusion criteria.

Admission criteria deviations will be presented in a data listing for the participants who randomized.

6.5. Genetics

Blood samples for genetic testing of CYP2C9 polymorphism will be collected at clinical Check-in (Day -1) for Period 1.

Genetic testing results will be listed and summarized by treatment sequence and overall for the safety set.

7. Treatments and Medications

7.1. Prior and Concomitant Medications

Prior medications are defined as medications that were started and ended prior to the first dose of treatment. Concomitant medications are defined as medications that were administered after the first dose of treatment. Medications initiated prior to the first dose of treatment and were continued after the first dose of treatment will be counted as both prior and concomitant medications.

Prior concomitant medications will be summarized by treatment sequence and overall for the safety set. Concomitant medications will be summarized by treatment and overall for the safety set. The anatomical therapeutic chemical code coding scheme of the World Health Organization Drug Dictionary Version March 2019 or later will be used to group medications into relevant categories for the tabulation.

All prior and concomitant medications will be presented in a data listing for the safety set.

7.2. Non-Pharmacologic Therapies and Procedures

Non-pharmacologic therapies and procedures will be coded using the MedDRA Version 23.0 or later and will be presented in a data listing for the safety set.

7.3. Study Treatments

Study treatments will be administered in each study period at the morning of Day 1 and all participants will receive 1 treatment in each study period. Study treatments are as follow

• Treatment A: One 200 mg celecoxib capsule with 240 mL water (fasting).

• Treatment B: One 200 mg celecoxib capsule $+4 \times 15$ mg ALXN1840 EC tablets with 240 mL water (fasting).

Any dose of ALXN1840 or celecoxib greater than that specified in the protocol will be considered an overdose.

Study treatment administration data will be presented in a data listing for the safety set.

8. Safety Analysis

All safety analyses will be performed on the safety set.

Safety analyses will include an analysis of all AEs, ECGs, clinical laboratory data, physical examinations, and vital sign measurements using descriptive statistics. Summaries will be presented by treatment and overall, unless otherwise stated. Shift tables will be summarized with count and percentages of participants in each category. Percentages will be based on the number of participants with both non-missing baseline and relevant post-baseline results.

No inferential statistical analyses are planned for the safety parameters of this study.

8.1. Adverse Events

An AE is any untoward medical occurrence in a participant, temporally associated with the use of study intervention, whether or not considered related to the study intervention. An AE can therefore be any unfavorable and unintended sign (including an abnormal laboratory finding), symptom, or disease (new or exacerbated) temporally associated with the use of study intervention.

Adverse events will be analyzed in terms of TEAEs which are defined as any AEs that begin or worsen on or after the first dose of treatment until the EOS or early termination (ET). If the onset date/time of an AE is missing and AE end date is on or after the first dose of treatment, the AE will be defined as treatment-emergent.

All AEs will be listed from the time the participant signs ICF until the EOS or ET Visit.

A treatment-related TEAE is defined as TEAE which was considered to be related to the treatment.

All AEs will be coded by SOC and PT using the MedDRA Version 23.0 or later.

All summary tables will include number and percentage of participants and number of events, unless otherwise stated. For the number of AEs, each occurrence will be counted once. Percentages will be based upon the number of participants in the safety set.

In the summary tables where both SOC and PT are presented, the default ordering of SOC will be alphabetical and the default ordering for PT will be most prevalent (using percentage) PT within each SOC based on Total column. For PTs with the same number of participants, they should be further sorted by number of events and then alphabetically.

In the by- participant analyses, a participant having the same event more than once within the same level of summarization will be counted only once within the same treatment using the most intense or worst highest event (for by toxicity grade summary) or the most related event (for by relationship summary).

In summaries of AEs by treatment, AEs will be summarized according to the most recent treatment received prior to the AE onset, regardless of when the AE ended. For example, an AE that started on or after administration of the treatment on Day 1 in Dosing Period 1 but before the administration of treatment on Day 1 in Dosing Period 2 will be summarized for the treatment in Period 1; an AE that started on or after administration of treatment on Day 1 in Dosing Period 2. The AEs that started before administration of treatment on Day 1 in Dosing Period 2. The AEs that started before administration of treatment on Day 1 in Dosing Period 1 will not be summarized unless if the AE meets the TEAE definition, in that case, the AEs will be summarized for the treatment received prior to the AEs worsened.

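### SAP 8.1, read literally, divides by-treatment AE counts by the whole safety set, so anyone dosed only in Period 1 dilutes the incidence of a treatment they never received

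*SAP*

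**What the plan says.** SAP 8 sets the layout of the safety tables: "Summaries will be presented by treatment and overall, unless otherwise stated". Within that layout, SAP 8.1 makes the numerator treatment-specific: "AEs will be summarized according to the most recent treatment received prior to the AE onset, regardless of when the AE ended".

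The denominator is given earlier in SAP 8.1: "Percentages will be based upon the number of participants in the safety set". SAP 4.4.3 defines the set: "The safety set will include all participants who receive at least 1 dose of study intervention". One dose of either treatment is enough.

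Three other places bear on the denominator:

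- SAP 4 has a general default: "The denominator for all percentages will be the number of participants in the treatment sequence for the population of interest, unless otherwise specified". SAP 8.1 specifies otherwise for AEs, so the default gives way. It would not give the number exposed to a treatment in any case.
- SAP 8 restricts shift-table percentages to participants with both baseline and later values. It has no comparable restriction for AEs.
- SAP 5.1 says: "Based on the randomized participants, the analysis sets will be summarized with counts and percentages by treatment and overall". The number in the safety set is one of the items counted, but no rule says how a participant is placed in a treatment column.

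Protocol 9.4.2 asks for AE incidence for each treatment and overall, and does not define a denominator.

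**The concern.** In a two-period crossover, an event can be counted under a treatment only after that treatment has been given. A participant who takes the Period 1 dose and leaves before Period 2 is in the safety set but was never at risk under the second treatment. If the whole safety set is the denominator of every column, that participant is counted there as someone who took the treatment and had no event.

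The incidence of TEAEs and TESAEs is a named secondary endpoint (SAP 3.3.2), so the by-treatment percentages will be read as incidences. The error has one direction: it lowers the figure for the treatment that was missed. A participant in sequence AB who leaves between doses dilutes column B, and one in sequence BA dilutes column A. If the two sequences lose different numbers, the columns carry different errors, and part of any gap between them comes from the denominator.

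**Working it through.** **Inputs**

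- Evaluable participants: 32 (SAP 4.2).
- Dropout and enrolment: "Assuming a 15% dropout rate, approximately 38 participants will be enrolled" (SAP 4.2).
- Allocation: 19 to AB and 19 to BA (SAP 3.1, Table 1).
- Assumption: all 38 are dosed in Period 1, so the safety-set N is 38. The documents do not say when dropout would occur, so the number lost between doses is varied below.

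**The plan's own figure.** 32/(1 − 0.15) = 37.6, rounded up to 38. This reproduces the stated enrolment. It allows for 38 − 32 = 6 dropouts.

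**Formula.** Let x be the number of participants with a TEAE under a treatment, N the safety-set size, and k the number in the safety set who never received that treatment.

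- Literal SAP 8.1 percentage: x/N
- Exposure-based percentage: x/(N − k)
- Ratio of the first to the second: (N − k)/N, so the relative understatement is k/N

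**Results for N = 38, with x = 8 as illustration**

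| k missing the treatment | Exposed | Ratio | Relative understatement | 8 participants, literal | 8 participants, exposure-based |
|---|---|---|---|---|---|
| 0 | 38 | 1.000 | 0% | 21.1% | 21.1% |
| 1 | 37 | 0.974 | 2.6% | 21.1% | 21.6% |
| 3 | 35 | 0.921 | 7.9% | 21.1% | 22.9% |
| 6 | 32 | 0.842 | 15.8% | 21.1% | 25.0% |

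The k = 3 row is what each column shows if all six planned dropouts leave between doses and split evenly by sequence. The k = 6 row is one column if all six come from the same sequence; the other column is then exact.

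**Effect on the comparison.** With an even split, both percentages are multiplied by 0.921. Their ratio is unchanged, and no gap appears where there was none. With all six from BA, column A is multiplied by 0.842 and column B by 1. For example, an incidence of 50% under both treatments (16 of 32 on A, 19 of 38 on B) would be reported as 16/38 = 42.1% for A against 19/38 = 50.0% for B.

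**Replacement.** Protocol 1.1 lets the sponsor replace participants. A dosed participant who is replaced stays in the safety set, so replacement enlarges N without removing the error. If six are lost from one sequence and six replacements complete both periods, N = 44, 38 have received the missed treatment, and the understatement is 6/44 = 13.6%.

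**The case against.** The strongest reply is that the SAP 8.1 sentence names the analysis set and leaves the column N to the table layout. SAP 8 lays tables out by treatment, and SAP 5.1 counts the safety set by treatment. In a crossover where everyone is assigned both treatments, that count is informative mainly if it reflects who received each one. A programmer could well use it by convention. This stands as a hint, but no more: SAP 5.1 gives no assignment rule, SAP 8.1 does not refer to it, and the literal text gives one N for all columns.

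The second reply is about size, and most of it stands. A reader might infer from the 15% dropout figure that about six participants will be lost between doses. The documents do not support that. The 15% is an allowance for reaching 32 in the PK comparison, and dropouts after Period 2 dosing do no harm here. Protocol 7.2 does not expect withdrawal to be common. Participants are resident to Day 11 of each period and may be kept in the unit between periods (Protocol 4.1).

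A reader might also infer that the rule would distort the A–B contrast because ALXN1840 in Period 1 would drive withdrawals. Protocol 9.7 and SAP 8.1.1 provide for withdrawal because of adverse events, but the documents give no rate, and Protocol 4.3 describes the 60 mg single dose as well tolerated. In that scenario the diluted column would be celecoxib alone, so the rule would not hide ALXN1840 events.

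Finally, the error is recoverable. AE tables also show numbers of participants and events, AEs and dosing are listed by participant, and no safety inference is planned. This stands, and it limits the severity.

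**Conclusion.** The point holds as a minor one. As written, SAP 8.1 pairs a treatment-specific numerator with a denominator that ignores treatment, and no other section corrects this. Any participant dosed in Period 1 but not in Period 2 lowers the reported TEAE incidence of the missed treatment.

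The size depends on the number lost between doses, which the documents do not give. With 38 dosed, it runs from zero with no such loss, through 2.6% relative for one participant and 7.9% for three, to 15.8% if all six planned dropouts leave between doses from one sequence. That last figure is the extreme of the planned dropout, not an expectation.

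It would go too far to say that incidence will be understated, or that the A–B comparison will be distorted. The first needs both the literal reading and between-dose dropout; the second also needs that dropout to differ by sequence. The overall column is right as it stands, and the primary PK analysis is unaffected.

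**What to change.** Replace the denominator sentence in SAP 8.1 with: *For each treatment column, percentages will be based on the number of safety set participants who received that treatment; for the overall column, on the number of participants in the safety set.* Show that N in each column header of the AE tables.

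The cost is one sentence in the SAP and column-specific Ns in the table shells. It needs no new data and no design change. Percentages change only for a treatment that someone in the safety set did not receive, and they become slightly higher.
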